A run in phase of cabozantinib at 40 mg/day will be performed for the first 6 patients, beginning in Cycle 1. If the combination is well tolerated the trial will complete accrual at this dose level. If the combination is not well tolerated, with 2 DLTs observed in the first 6 patients, the dose of cabozantinib will be decreased to 20 mg/day which will be the dose used for the rest of the study.

Phase II:

Pembrolizumab will be administered at the standard dose of 200 mg Q 3 weeks. Cabozantinib will be given at the dose determined in the run in phase. Both agents will be initiated on Day 1 of Cycle 1 and will continue in combination.

NUMBER OF SUBJECTS

The sample size will be up to 34 subjects in which the first 6-9 patients will be in the safety run-in phase with an interim futility assessment after 20 patients were treated.

TARGET POPULATION

Cancer patients will be eligible for enrollment as defined by the inclusion and exclusion criteria as follows:

Inclusion Criteria

1. The subject has a histologic or cytologic diagnosis of squamous cell carcinoma of the oral cavity, oropharynx, paranasal sinuses, hypopharynx, nasopharynx or larynx. Squamous cell carcinoma of unknown primary in cervical lymph node can be included only if HPV status is positive.
2. Patients must have refractory, recurrent or metastatic disease, which is deemed to be inoperable.
3. In case patients received prior systemic therapy within the definitive or metastatic setting, disease progression must be documented following prior therapy; this can be in the recurrent or metastatic setting or in the concurrent setting.
4. Measurable disease per RECIST 1.1 as determined by the investigator;
5. A maximum of one prior radiotherapy regimen, curative or palliative, to the head and neck is allowed. If the radiation is combined with chemotherapy, a minimum of 4 months must elapse between the end of radiotherapy and registration. If the radiation is given alone, a minimum of 8 weeks must elapse between the end of radiotherapy and registration. A minimum of 3 weeks must elapse between prior radiation to other areas and registration. Treatment areas should be healed with no sequelae from RT that would predispose to fistula formation
6. The subject has had an assessment of all known disease sites eg, by computerized tomography (CT) scan, magnetic resonance imaging (MRI), bone scan or PET/CT scan as appropriate, within 28 days before the first dose of cabozantinib;

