2.2 Study Design

2.2.1 Overview of Study Design

All patients will require measurable disease by RECIST 1.1 and will need documentation of disease progression after platinum based therapy; archival tissue will need to be submitted; if archival tissue is not possible a fresh biopsy is mandated.

Run-in phase:

Pembrolizumab will be initiated in Cycle 1 at the standard dose of 200 mg Q 3 weeks for one cycle.

A run in phase of cabozantinib at 40 mg/day will be performed for the first 6 patients, beginning in Cycle 1. If the combination is well tolerated (<2 DLTs in the first cycle), the trial will complete accrual at this dose level. If the combination is not well tolerated, with 2 DLTs in the first treatment cycle observed in the first 6 patients, the dose of cabozantinib will be decreased to 20 mg/day which will be the dose used for the rest of the study.

DLT Criteria

Adverse events (AEs) will be graded in accordance to the National Cancer Institute Common Terminology Criteria for Adverse Events (CTCAE) (v4.0). Dose-limiting toxicity (DLT) is defined as any of the following treatment-related AEs occurring during the DLT Evaluation Period, which will be during the first cycle of combined pembrolizumab and cabozantinib.

- Treatment-Related Non-Hematologic AEs:
 1. Any related \geq Grade 3 AE which is unexpected in severity and/or duration compared to the known safety profiles of cabozantinib and pembrolizumab when used as single agents, and that cannot be managed by dose modification (reduction or interruption) and adequate supportive care, and requires permanent discontinuation of cabozantinib and/or pembrolizumab.

2. Inability to take $\geq 75\%$ of the total planned cabozantinib dose for the DLT Evaluation Period because of a treatment-related AE leading to dose reductions and/or interruptions

For the AEs described in Section 3.3.2 - 3.3.2.19, the specific AE management guidelines in this section should be followed to determine the need for dose reductions and dose interruption.

- Treatment-Related Hematologic AEs:
 1. Grade 3 neutropenia of ≥ 7 days duration or any Grade 4 neutropenia
 2. \geq Grade 3 febrile neutropenia;
 3. All other hematologic toxicities of Grade 4 (except anemia as described in Section 3.3.2.4)

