A subject will be replaced if the subject does not have a DLT but is not fully evaluable for DLT due missing more than 25% in total of the dosing days due to progressive disease or for reasons other than cabozantinib-related toxicity.

Each subject's course will consist of three periods:

- A Pre-Treatment Period in which subjects are consented and undergo screening assessments to be qualified for the study (Section 16.o);
- A Treatment Period in which subjects receive study treatment and undergo study assessments (Section 16.o);
- A Post-Treatment Period in which subjects no longer receive study treatment but undergo follow-up study assessments and contacts (Section 16.o).

Phase II:

Pembrolizumab will be administered at the standard dose of 200 mg Q 3 weeks. Cabozantinib will be given at the dose determined in the run in phase. Both agents will be initiated on Day 1 of Cycle 1 and will continue in combination for the rest of the study.

Patients will be evaluated every 3 weeks on the study with a physical exam, clinic visit. CT scans MRIs or PET/CT will be required for staging every 9 weeks.

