When cabozantinib or pembrolizumab are discontinued for reasons deemed to be related to one or the other agent, the protocol calls for the discontinuation of both agents until and when the toxicities have reached a tolerable level (as specified in the dose modification sections) at which time both agents will be re-initiated. Patients who have interruption of both agents for more than 6 consequential weeks will be removed from the study; response assessment for these patients will still be assessed if available; in addition to assessment of OS and PFS based on the intent to treat analysis principle.	Assigned dose	First Dose Level Reduction
	40-mg cabozantinib oral qd	20-mg cabozantinib oral qd

Table 3-3: Dose Modifications of Cabozantinib for Treatment-Related AEs

CTCAE v.4.0 Grade	Recommended Guidelines for Management ^a
Grade 1 AEs	Add supportive care as indicated. Continue cabozantinib treatment at the current dose level if AE is manageable and tolerable.
Grade 2 AEs which are tolerable and are easily managed	Continue cabozantinib treatment at the current dose level with supportive care.
Grade 2 AEs which are intolerable and cannot be adequately managed	At the discretion of the investigator, cabozantinib should be dose reduced or interrupted. Note: It is recommended that dose holds be as brief as possible.
Grade 3 AEs (except clinically non-relevant laboratory abnormalities)	Cabozantinib should be interrupted unless the toxicity can be easily managed with a dose reduction and optimal medical care. Note: It is recommended that dose holds be as brief as possible.
Grade 4 AEs (except clinically non-relevant laboratory abnormalities)	Subjects should have cabozantinib interrupted immediately. Discontinue cabozantinib unless the following criteria are met: 
• Subject is deriving clear clinical benefit as determined by the investigator and agreed by the Sponsor• Toxicity can be managed with a dose reduction following recovery to Grade 1 (or baseline) and optimal medical care

AE, adverse event.

Note: The dose delay and modification criteria for specific medical conditions are provided in Section 3.3.2. For re-treatment criteria of study treatment after a dose hold see Section 3.3.1.1.

^a Study treatment dose adjustment is only needed if the toxicity was deemed related to cabozantinib treatment or had an unclear relationship to cabozantinib treatment.

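### A run-in patient on half doses with no day missed, for a cause not judged treatment-related, is neither a DLT nor replaced, because the two rules use different measures

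*Combined protocol and SAP*

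**What the plan says.** Section 2.2.1 plans the run-in as follows: "A run in phase of cabozantinib at 40 mg/day will be performed for the first 6 patients, beginning in Cycle 1". The decision rule is "If the combination is well tolerated (<2 DLTs in the first cycle), the trial will complete accrual at this dose level"; with 2 DLTs the cabozantinib dose is lowered for the rest of the study.

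Two rules in that section deal with patients who do not take the full first-cycle dose:

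- **DLT criteria, non-hematologic item 2.** The patient is a DLT if unable to take at least 75% "of the total planned cabozantinib dose for the DLT Evaluation Period because of a treatment-related AE leading to dose reductions and/or interruptions". The unit is dose, reductions count, and the cause must be a treatment-related AE.
- **Replacement.** "A subject will be replaced if the subject does not have a DLT but is not fully evaluable for DLT" on account of "missing more than 25% in total of the dosing days due to progressive disease or for reasons other than cabozantinib-related toxicity". The unit is days missed, and the cause must be progression or anything other than cabozantinib-related toxicity.

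No other section defines DLT evaluability. The only other definition of an evaluable subject, under Sample Size in Section 18, concerns the response endpoint and requires a follow-up scan.

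**The concern.** The two rules ought to be complements. A patient who took clearly less than the planned cabozantinib, and so says little about tolerance of the starting dose, should be either a DLT or replaced. Because one rule counts milligrams and the other counts days, a patient can fall well short on dose while missing no day. If the shortfall was not caused by a treatment-related AE, item 2 does not apply either. The patient then stays among the six and adds a non-DLT to the count.

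The run-in has only six patients and its result fixes the dose for everyone who follows, so one such patient matters, and the error always runs toward passing. Section 3.3.2 adds that most subjects need 2 to 3 weeks to reach steady state, which is about the whole DLT window. A patient on half doses for most of that time has had little exposure at the level under test.

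**Working it through.** **Inputs.** Cycle of 21 days (Study Assessments table, Section 16); starting dose 40 mg/day and one reduction level of 20 mg/day (Section 3.3, Table 3-2); 20-mg tablets (Section 3.1.2); run-in of 6 patients, passed with fewer than 2 DLTs (Section 2.2.1). The documents state no DLT rate and no error rate for the run-in, so there is no figure of the plan's own to reproduce. I assume true DLT rates from 0.20 to 0.40.

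**Planned dose.** 21 × 40 = 840 mg.

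**Case 1: whole days missed, single cause.**
- 5 days missed: 16/21 = 76.2% of dose and 5/21 = 23.8% of days. Neither threshold is crossed, consistently.
- 6 days missed: 15/21 = 71.4% of dose and 6/21 = 28.6% of days. Both are crossed: a DLT if treatment-related, replaced if not.

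There is no gap here.

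**Case 2: 20 mg taken instead of 40 mg on k days, cause not judged treatment-related.** Share of dose = (840 − 20k)/840; days missed = 0 (a reduced-dose day read as not missed).
- k = 10: 640/840 = 76.2%, above the threshold.
- k = 11: 620/840 = 73.8%.
- k = 20: 440/840 = 52.4%.
- k = 21: 420/840 = 50.0%.

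For k from 11 to 21 the patient is below 75% of dose, is not a DLT under item 2 (wrong cause) and is not replaced (no day missed). This is the gap.

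**Case 3: whole days missed, two causes.** Let a days be missed for a treatment-related AE and b days for another reason. If each rule counts only its own cause, neither applies when a ≤ 5 and b ≤ 5, yet the dose is below 75% when a + b ≥ 6. That gives 5 + 4 + 3 + 2 + 1 = 15 combinations (a + b = 6, 7, 8, 9, 10). The most extreme is 5 + 5, which leaves 11/21 = 52.4% of dose. If missed days are pooled, or if any decisive treatment-related contribution makes a DLT, the combinations are classified and this gap closes.

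**Effect on the run-in decision.** With n informative patients and true DLT rate p, the chance of passing is (1 − p)^n + n·p·(1 − p)^(n − 1). Six properly dosed patients give n = 6. If one of the six is a gap patient assumed unable to show a DLT, n = 5.

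| True DLT rate (assumed) | 6 informative | 5 informative + 1 gap patient | Difference |
|---|---|---|---|
| 0.20 | 0.655 | 0.737 | 0.082 |
| 0.25 | 0.534 | 0.633 | 0.099 |
| 0.33 | 0.358 | 0.468 | 0.110 |
| 0.40 | 0.233 | 0.337 | 0.104 |

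Worked line at 0.20: 0.8^6 + 6 × 0.2 × 0.8^5 = 0.262 + 0.393 = 0.655, and 0.8^5 + 5 × 0.2 × 0.8^4 = 0.328 + 0.410 = 0.737 (from unrounded terms).

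**The case against.** The best reply is that the gap is close to hypothetical. Footnote a of Table 3-3 says cabozantinib adjustment is needed only for toxicity related to cabozantinib or of unclear relationship. Section 3.3 treats reductions as toxicity management, and Section 3.3.2 presumes adverse reactions to be attributable to study drug. A reduction for a related AE that takes intake below 75% is already a DLT. The example given in Section 3.3 of a non-AE cause, a surgical procedure, concerns an interruption, and whole missed days with one cause are classified without a gap.

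Most of this stands, and it limits how often the gap will occur. It does not close it. The footnote does not forbid other reductions, and Section 3.3 allows doses to be modified at any time. No investigator decision is even needed: 40 mg is two 20-mg tablets, and a patient who takes one a day by mistake receives 50.0% with no day missed. Section 17 also defines an unrelated event more loosely than Section 3.3.2 does, so the presumption of attribution is not a firm safeguard.

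It is also fair to say that the table above is an upper bound. A gap patient can still be a DLT under non-hematologic item 1 or the hematologic criteria.

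Two stronger readings are tempting and should not be adopted.

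- **Pembrolizumab toxicity.** Section 3.3 says that, for toxicity of either drug, "the protocol calls for the discontinuation of both agents until and when the toxicities have reached a tolerable level". A reader might infer that patients taken off cabozantinib for a pembrolizumab toxicity are replaced rather than counted. The text does not support this. The DLT window is the first cycle of the combination, item 1 refers to the safety profiles and discontinuation of both drugs, and replacement requires that the subject has no DLT. The two cause clauses overlap on pembrolizumab-only toxicity, and DLT status settles the overlap.
- **Mixed causes.** A reader might call the 5 + 5 patient a certain gap. But without the related AE that patient would have taken 76.2%, so the shortfall can reasonably be read as due to it, which makes a DLT. The replacement rule's reference to a total can also be read as pooling all missed days. The case is ambiguous, not a proven gap.

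**Conclusion.** The concern holds in a limited form. The DLT criterion and the replacement rule use different measures, and reduced-dose days for a cause not judged treatment-related fall between them. That the patient then counts as a non-DLT follows by default from the two-DLT rule; no sentence in the protocol says that such a patient tolerated 40 mg.

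One such patient among six adds at most about 8 to 11 percentage points to the chance of passing, for true DLT rates of 0.20 to 0.40. This rests on three assumptions: the DLT rate, the presence of one gap patient, and that patient's inability to show a DLT under any criterion. The case should be uncommon, and nothing in the documents suggests that several of the six would be affected. The change is worth making because the bias has one direction, the sample is six, and the correction is cheap.

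**What to change.** Reconcile the DLT criteria and the replacement rule in Section 2.2.1 so that both use the measure already in item 2. For example: a subject is evaluable for DLT if he or she had a DLT, or took at least 75% of the total planned cabozantinib dose in mg during the DLT evaluation period; a subject without a DLT who took less, for whatever cause or combination of causes, is replaced.

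Add three clarifications:

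1. DLT status is decided first, and replacement is considered only afterwards.
2. Treatment-related, in item 2, means related to either study drug.
3. A stated rule says how a shortfall partly due to a treatment-related AE is classified. Without it, pooling all causes could simply replace a patient who was under-dosed in part by related toxicity, which would bring back the same bias. The choice belongs to the sponsor; it needs to be made before the run-in is read.

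The run-in size should be aligned at the same time. Section 2.2.1 and the statistical sections give 6, while the synopsis under Number of Subjects says "the first 6-9 patients will be in the safety run-in phase", which already leaves room for replacements.

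The cost is a few sentences and, occasionally, one more run-in patient to replace. The 75% threshold, the doses and the two-DLT rule are left as they are.

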2.3 Treatment Assignment

It is the responsibility of the investigator to assign a subject number before treating each subject with cabozantinib.

2.4 Blinding and randomization

Not applicable.

2.5 Study Sites

This study will be conducted at up to 2 sites: Emory Winship Cancer Institute and Moffitt Cancer Center.

2.6 Registration

Pre-registration: Emory: Pre-registration must be completed and sent to the Central Subject Registrar and to the Office of Clinical Research. After receipt of the pre-registration form and confirmation of a valid, signed informed consent form/HIPAA authorization form, the Winship Clinical Trials office will assign a patient study number.

Participating site(s): After each subject signs consent, the Central Subject Registration form is to be completed and sent to Winship Clinical Trial Office within 48 hours of consent. This form, along with the valid, signed informed consent form/HIPAA authorization form, is to be faxed or emailed to Winship's Central Subject Registrar per instructions on the form. The Winship Clinical Trials office will assign a patient study number to these patients.

Patient study number assignment/confidentiality: Subjects will be assigned a coded designation according to the site at which the subject signs consent. Actual names, contact information and relationship to this code will be kept secure in the Winship Clinical Research Office.

Registration: Participating site(s): The Eligibility checklist is to be printed from OnCore and verified by 2 people, of which one must be a clinical investigator or co-investigator. The completed and signed eligibility checklist along with all redacted supporting source documentation must be submitted to the Winship Multi-site Coordinator or designee ([contact]) within 14 days after pre-registration but no later than 2 business days from scheduled treatment visit. Eligibility will be confirmed by a clinical principal or co-investigator and the Multi-site Coordinator or designee within 2 business days of receipt of all eligibility documentation and confirmation will be sent to the participating site along with cohort assignment, if subject meets criteria. Once eligibility is confirmed, then patient will be registered and scheduled for appropriate appointments.

2.7 Withdrawals

Subjects may discontinue study treatment or withdraw their consent to participate in the study at any time without prejudice. The investigator may withdraw a subject from study treatment or from the study if, in his or her clinical judgment, it is in the best interest of the subject or if the subject cannot comply with the protocol.

In addition, any of the following conditions require discontinuation of the subject from study treatment:

- An AE or intercurrent illness that in the opinion of the investigator warrants the subject's withdrawal from study treatment;
- The investigator believes it is not in the best interest of the subject to continue on study
- Specific conditions described in the Management of Adverse Events Sections 3.3.2 and 3.3.2.1;
- Necessity for treatment with other anticancer treatment prohibited by protocol;
- Sexually active subjects who refuse to use medically accepted barrier methods of contraception (eg, male condom, female condom) during the course of the study and for 4 months after discontinuation of study treatment;
- Women who become pregnant or are breastfeeding;
- If the subject does not recover from his or her toxicities to tolerable Grade ≤ 2 within 6 weeks, the subject will have study treatment discontinued unless there is unequivocal evidence that the subject is benefitting. In this situation, a subject may be able to restart therapy with a dose reduction upon resolution of the toxicity and with agreement of the principal investigator / Sponsor;
- Request by regulatory agencies for termination of treatment of an individual subject or all subjects under the protocol;
- Significant noncompliance with the protocol schedule in the opinion of the investigator;
- The minimum dose of study treatment will be 20 mg once daily (qd). Subjects who cannot tolerate 20 mg qd will have study treatment discontinued;

- Progressive disease (PD) or the subject no longer experiences clinical benefit as determined by the investigator

3 TREATMENTS

3.1 Composition, Formulation, and Storage

At study sites, all study medication will be stored as described in the pharmacy manual and inventoried in accordance with applicable state and federal regulations.

3.1.1 Investigational Treatment

Chemical Name: Chemical Name: *N*-{4-[(6,7-dimethoxyquinolin-4-yl)oxy]phenyl}-*N'*-(4-fluorophenyl)cyclopropane-1,1-dicarboxamide, (2S)-hydroxybutanedioate

3.1.2 Cabozantinib Tablets

Exelixis internal number: XL184

Cabozantinib tablets are supplied as film coated tablets containing cabozantinib malate equivalent to 20 mg of cabozantinib and contain microcrystalline cellulose, lactose anhydrous, hydroxypropyl cellulose, croscarmellose sodium, colloidal silicon dioxide, magnesium stearate and Opadry® yellow. All tablet strengths are prepared from a common blend and are distinguished by shape. The 20 mg tablets are round. The components of the tablets are listed in Table 3-1.

Table 3-1: Cabozantinib Tablet Components and Composition

Ingredient	Function	% w/w
Cabozantinib malate (25% drug load as cabozantinib)	Active Ingredient	31.7
Microcrystalline Cellulose (Avicel PH-102)	Filler	38.9
Lactose Anhydrous (60M)	Filler	19.4
Hydroxypropyl Cellulose (EXF)	Binder	3.0
Croscarmellose Sodium (Ac-Di-Sol)	Disenegrant	6.0
Colloidal Silicon Dioxide,	Glidant	0.3
Magnesium Stearate	Lubricant	0.75
Opadry Yellow Film Coating which includes:		
- HPMC 2910/Hypromellose 6 cp		
- Titanium dioxide	Film Coating	4.00
- Triacetin		
- Iron Oxide Yellow		

3.2 Dose, Schedule and Route

Subjects will receive cabozantinib orally at a (starting) dose of 40 mg once daily.

Cabozantinib must be taken on an empty stomach. Subjects must be instructed not to eat for at least 2 hours before and at least 1 hour after taking cabozantinib. Subjects should be instructed to take their cabozantinib dose at approximately the same time every day. If a subject misses a dose, the dose may be taken later only if it is within 12 hours of when the missed dose should have been taken. The missed dose should not be made up if it is within 12 hours of the next scheduled dose.

Cabozantinib tablets should be swallowed whole with at least 8 ounces of water. The tablets should not be crushed. Grapefruit, grapefruit juice, Seville oranges and their products should be avoided by subjects taking cabozantinib.

In all subjects, dose reductions and delays to manage toxicity are allowed under the guidelines in Section 3.3 below.

